### **12.10 Audit and inspection**

All source data and all trial data and material will be made directly available for audit and inspection. Source data is all information in original records and certified copies of original records that is necessary for the reconstruction and evaluation of the trial.

### **12.11 Handling of patient data**

All patients will be assigned a unique code number. The patient data will be linked to this number, and the patients' names or other personal identifiers will not be included in the database. The patient database will be kept on a separate, secure computer. The code will be stored on another, secure computer, and will be deleted 15 years after the results of the trial have been published. The trial's procedures for data protection will conform to the Norwegian applicable regulatory requirements, and to the conditions set by the Norwegian Data Inspectorate.

### **12.12 Handling of the list of treatment codes**

The lists of random treatment codes will be produced by the Statistical Centre at the University of Tromsø. Copies of the list will be kept by the person setting up the central randomisation system, and the Trial Statistical Centre. The list will be kept secret for all other people involved in the trial until the closure of the patient database.

### **12.13 Screening logs**

Participating centres will be asked to make records of all patients considered for inclusion in the trial (screening logs).

### **12.14 Financial conduct**

Contracts will be agreed between the Sponsor and each of the investigators/institutions. The Coordinating Investigator or other people centrally involved in the trial will not have any financial or other conflicts of interest in connection to the trial. Patients participating in the trial will be reimbursed for their travel expenses.

### **12.15 Publication and data sharing policy**

The trial will be published in accordance with the CONSORT guidelines and will be presented by a writing committee on behalf of the investigators. All participating centres and collaborators will be acknowledged in the main publication. The primary results and results of any substudies will be presented at international meetings and in public media.

### **12.16 User involvement**

The Patient Advisory Board consists of representatives from two stroke patient organisations in Norway, with [name] from Norsk forening for slagrammede, and [name] from Hjerneslag. The board will be consulted in all phases of the study.

## **13. Central trial organisation**

### **13.1 Sponsors and funding bodies**

The University Hospital of North Norway is the Sponsor of the trial. Address: [name]. [contact]. The Director of Research will act as the Sponsor's legal representative.

The trial receives basic funding from the Norwegian Ministry of Health and Care Services (Clinical Therapy Research in the Specialist Health Services Research Programme (KLINBEFORSK )) and the National Association for Public Health. The trial also receives funding from the British Heart Foundation and from the Swiss Heart Foundation. Boehringer-Ingelheim GmbH will reimburse the Sponsor for the costs of tenecteplase.

### **13.8 Event Adjudication Committee**

To be appointed.

## **14. Time table and end of trial**

First patient included: July 2017

Last patient included: September 2021

End of follow-up: December 2021

Presentation of main results: 2022

Follow-up by record linkage with central registries: December 2025

The end of the trial is defined as the last visit of the last patient included.

## 16. Appendix

### 16.1 Completed and on-going studies of thrombolytic treatment for wake-up stroke

Trial (clinicaltrials.gov ID)	Planned enrolment	Participants	Interventions	Primary outcome	Recruitment period
WAKE-UP (NCT01525290)	800 (503 enrolled)	Ischaemic stroke; <4.5 hours after awakening; MRI DWI/FLAIR mismatch	1. IV alteplase 2. Placebo	mRS score at 90 days	Nov 2012 – June 2017
WASSABI (NCT01455935)	90	Ischaemic stroke on wake-up; <24 h of onset; NIHSS 8-22; 18-80 years; Penumbra on CT perfusion	1. Best medical care 2. IV alteplase 3. IA treatment	mRS score at 90 days	Nov 2011 –
EXTEND (NCT01580839)* *Not a study of wake-up stroke per se, but 146 (65%) of the included patients had wake-up stroke.	400, revised target 310 (225 enrolled)	NIHSS 4-26; Penumbra mismatch on MRI or CT	1. IV alteplase 2. Placebo	mRS score at 90 days	June 2010 – June 2018
THAWS (NCT02002325)	300 (131 enrolled)	Initial NIHSS $\geq 5$ and $\leq 25$ ; DWI/FLAIR mismatch on MRI	1. IV alteplase 2. Control	mRS at 90 days	April 2014 – July 2018

### 16.2 Definitions of clinical events

#### 16.2.1 Serious adverse events

A serious adverse event is any untoward medical occurrence that, at any dose:

- results in death
- is life threatening
- requires hospitalisation or prolongation of an existing hospitalization
- results in disability/incapacity
- is a congenital abnormality / birth defect.

Medical and scientific judgement should be exercised in deciding whether reporting is appropriate in other situations, such as important medical events that may not be immediately life-threatening or result in death or hospitalisation, but may jeopardise the subject or may require medical or surgical intervention to prevent one of the other outcomes listed in the above definition. These should also be considered serious. Examples of such events are invasive or malignant cancers, intensive treatment in an emergency room or at home for allergic bronchospasm, blood dyscrasias or convulsions that do not result in hospitalisation, or development of drug dependency or abuse.

#### 16.2.2 Death

Death will be classified according to cause:

1. Initial stroke
2. Recurrent stroke
3. Myocardial infarction
4. Infection
5. Other vascular cause (e.g. systemic emboli)

6. Other non-vascular cause (e.g. malignancy, trauma)
7. Unknown cause

### 16.2.3 Recurrent stroke

Neurological deterioration (increase of  $\geq 2$  on NIHSS, after exclusion of other causes for neurological deterioration) occurring after 72 hours will be considered as a recurrent stroke. Recurrent stroke will be classified as ischaemic, haemorrhagic or unknown (if not documented on imaging).

### 16.2.4 Symptomatic intracranial haemorrhage (SICH)

The IST-3 and SITS-MOST definition of symptomatic intracranial haemorrhage are used:  
**SICH per IST-3:** symptomatic intracranial haemorrhage is defined as clinically significant deterioration (neurological deterioration, new headache, new acute hypertension, new nausea or vomiting, or sudden decrease in conscious level) or death within the first seven days of treatment with evidence of either significant brain parenchymal haemorrhage (local or distant from the infarct) or significant haemorrhagic transformation (HT) of an infarct on brain imaging.  
**SICH per SITS-MOST:** SICH is defined as local or remote parenchymal haematoma type 2 on the imaging scan obtained 22-36 hours after treatment, plus neurological deterioration, as indicated by an increase in National Institutes of Health Stroke Scale (NIHSS) score of  $\geq 4$  points compared to baseline value or the lowest value between baseline and 24 ( $\pm 6$ ) hours, or haemorrhage leading to death.

**Parenchymal haematoma type 2** indicates a haematoma exceeding 30% of the infarct, with obvious mass effect.

### 16.2.5 Asymptomatic intracranial haemorrhage

Intracranial haemorrhage on brain MRI or CT without: neurological deterioration, new headache, new acute hypertension, new nausea or vomiting or sudden decrease in conscious level.

### 16.2.6 Neurological deterioration due to index stroke

The definition is an increase of  $\geq 2$  points in one or more of the NIHSS (irrespective of improvement in any of the other NIHSS sub-scores). When diagnosing neurological deterioration due to index stroke, systemic reasons for deterioration, such as drug-induced hypotension, drug-induced drowsiness, and intercurrent disease should be excluded. No significant haemorrhage should be found on post randomization CT or MR scan.

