## 3. Background and rationale

### 3.1 Introduction

Thrombolytic treatment with recombinant tissue plasminogen activator (rt-PA) given within 4.5 hours of onset improves clinical outcome after ischaemic stroke, despite an increased risk of intracranial haemorrhage. Patients who have new stroke symptoms when they wake up from sleep (“wake-up stroke”) are excluded for such treatment, because the time of stroke onset is unknown. About one in five strokes occur during sleep, and it is unknown whether patients with wake-up stroke will benefit from thrombolytic treatment.

There are reasons to expect that patients with wake-up stroke will benefit from treatment. Several studies have shown that the onset of stroke during sleep is close to awakening, and that patients with wake-up stroke share many clinical and radiological findings with patients with stroke duration less than 4.5 hours. Studies have also shown that thrombolytic treatment is safe in patients with wake-up stroke up to 4.5 hours from wakening, and recently the WAKE-UP trial showed benefit of treatment with alteplase in patients selected based on DWI/FLAIR mismatch on MRI. In a Cochrane systematic review we have identified only one completed, small randomised-controlled trial of only nine patients. Two trials have recently been completed (EXTEND, THAWS,) and one is on-going (WASSABI, see Appendix). All these three trials use alteplase, and all use advanced imaging techniques for selection of patients. We will use a different strategy, and perform a large trial of tenecteplase, using a pragmatic study design, without exclusion of patients based on MRI findings. The trial will be complementary to the other trials, and is planned in advance to be included in our Cochrane meta-analysis of all trials of thrombolytic treatment for wake-up stroke, so that smaller, but still worthwhile effects can be detected that may be missed by the individual trials.

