**Data from clinical studies**

Tenecteplase is preferred over alteplase for treatment of myocardial infarction, because it has lower risk of bleeding complications, and because of the pharmacological advantages listed above.

A number of observational studies in patients with ischaemic stroke have shown that, compared to alteplase, tenecteplase is associated with similar or better recanalisation rates and clinical outcomes, and a similar or lower risk of intracranial haemorrhage. These studies have also concluded that the optimal dose of tenecteplase for stroke is 0.25 mg/kg.

[figure not shown]
There has also been three small randomised-controlled trials of tenecteplase vs. alteplase in acute ischaemic stroke. Meta-analysis of these trials with a total of 283 patients have shown that 76/178 patients (43%) patients given tenecteplase (doses ranging from 0.1 to 0.4 mg/kg) achieved good functional outcome (mRS score 0-1), compared to 33/105 patients (31%) patients given alteplase (odds ratio (OR) 1.39, 95% confidence interval (CI) 0.82-2.36, Figure 1).

**Figure 1.** Good functional outcome (mRS score 0-1) at three months

[figure not shown]

There was also a non-significant lower risk of symptomatic intracranial haemorrhage in patients given tenecteplase (Figure 2). The risks were 7/131 (5%) in patients given tenecteplase and 4/56 (7%) in patients given alteplase (OR 0.71, 95% CI 0.11-4.42). ATTEST 2014 did not provide data on symptomatic intracranial haemorrhage.

**Figure 2.** Symptomatic intracranial haemorrhage

There was no significant difference in the risk of death at three months (Figure 3). In total, 24 of the 178 patients (13%) given tenecteplase and 17 of the 123 patients (14%) given alteplase were dead at three months (OR 1.00, 95% CI 0.52-1.95).

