### 10.2 Secondary effect variables

#### *Clinical events:*

- Any intracranial haemorrhage during follow-up
- Symptomatic intracranial haemorrhage by SITS-MOST definition
- Symptomatic intracranial haemorrhage by IST-3 definition
- Parenchymal haemorrhage type 2Stroke progression during follow-up
- Recurrent ischaemic stroke during follow-up
- Major extra cranial bleeding
- Death from all cause during follow-up

Clinical events are defined in the Appendix.

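### The stroke-progression rule in Protocol 16.2.6 drops a deterioration whenever significant haemorrhage appears on a post-randomisation scan, even if the bleed neither preceded nor explains it, so the comparison can lean toward tenecteplase

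*Protocol*

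**What the plan says.** Protocol 10.2 lists "Stroke progression during follow-up" among the secondary clinical events and adds: "Clinical events are defined in the Appendix". No Appendix entry carries that name. The nearest is 16.2.6, neurological deterioration due to index stroke, so the link is an inference, though I see no other candidate. The Combined protocol and SAP lists the same event in its 10.2, and its Appendix has no entry that could define it.

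Section 16.2.6 has three parts:

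- **Score.** A rise of at least 2 points in one or more NIHSS items, "irrespective of improvement in any of the other NIHSS sub-scores".
- **Other causes.** Systemic explanations are to be ruled out.
- **Haemorrhage.** "No significant haemorrhage should be found on post randomization CT or MR scan".

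The entry does not define significant, gives no time window, and does not link the scan to the deterioration. Every patient has a CT at 24±6 hours (9.1), and every neurological deterioration leads to an emergency head CT (8.4).

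On the effect of treatment, 3.1 says that rt-PA improves outcome "despite an increased risk of intracranial haemorrhage". Section 12.6 has all events adjudicated centrally and blind.

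**The concern.** The third condition is decided after randomisation by a finding that treatment probably affects. Take a patient who worsens because of the infarct and later shows haemorrhagic transformation on the routine scan. As written, that patient is not a progression case. If such findings are more frequent on tenecteplase, more true progressions are struck out of that arm, and the drug can appear to prevent progression when it does not.

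Blinded adjudication does not cure this. The committee would apply the same rule to both arms, and the rule itself requires the removal. At stake is the meaning of one secondary comparison that readers will take as evidence on early worsening.

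**Working it through.** **1. Is there a stated figure to reproduce?** None for stroke progression: the documents give no rate, effect size or power for it. The only sample-size figure is for the primary outcome (Protocol 11.1). I checked it with the proportional-odds formula N = 12(z₀.₉₇₅ + z₀.₈₀)² / [ln(OR)² × (1 − Σp̄ᵢ³)], using the control distribution 15/27/23/17/13/5%, OR 1.50 and 1:1 allocation, with p̄ᵢ the mean of the control and shifted distributions. The result is N = 600.8, against 600 stated. It reproduces and does not depend on 16.2.6.

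**2. Which patients does the haemorrhage sentence remove?**

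- Deterioration caused by haemorrhage. Removal fits the heading, which is specific to the index stroke.
- Infarct-driven deterioration with haemorrhage seen later or incidentally. Removal does not fit the heading. Only this group distorts an index-stroke comparison.

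**3. How large could the distortion be?** Inputs:

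- 300 per arm (Protocol 11.1).
- True index-stroke progression p, the same in both arms: 8%, 12% or 16% (assumed).
- Significant haemorrhage h: 1% on control, 3% or 5% on tenecteplase (assumed). The only tenecteplase anchor is symptomatic haemorrhage in 3.2: "The risks were 7/131 (5%) in patients given tenecteplase". The comparator there was alteplase, and no untreated rate is given.

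Two limiting cases:

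- Haemorrhage independent of progression: counted events = 300 × p × (1 − h).
- Full overlap, with every haemorrhage in a patient who would have progressed from the infarct: counted events = 300 × (p − h).

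The true odds ratio is 1.00 in every row.

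| p, both arms | h, control / tenecteplase | Independent: events, apparent OR | Full overlap: events, apparent OR |
|---|---|---|---|
| 8% | 1% / 3% | 23.8 v 23.3, 0.98 | 21 v 15, 0.70 |
| 8% | 1% / 5% | 23.8 v 22.8, 0.96 | 21 v 9, 0.41 |
| 12% | 1% / 3% | 35.6 v 34.9, 0.98 | 33 v 27, 0.80 |
| 12% | 1% / 5% | 35.6 v 34.2, 0.95 | 33 v 21, 0.61 |
| 16% | 1% / 3% | 47.5 v 46.6, 0.98 | 45 v 39, 0.85 |
| 16% | 1% / 5% | 47.5 v 45.6, 0.95 | 45 v 33, 0.70 |

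Example, 12% with 1% / 5% and full overlap: (0.07/0.93) / (0.11/0.89) = 0.61. With equal haemorrhage rates in the two arms the apparent OR is 1.00.

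**4. Why compare deterioration of any neurological cause?** Suppose infarct-driven deterioration is 12% on control and 10% on tenecteplase, and haemorrhagic deterioration is 1% and 5% (assumed, in separate patients). The index-stroke count gives (0.10/0.90) / (0.12/0.88) = 0.81. Counting both causes, 13% against 15%, gives (0.15/0.85) / (0.13/0.87) = 1.18. The first figure is correct for its narrow question, but under the name stroke progression it would be read as less worsening overall.

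**The case against.** The case for leaving the rule alone is substantial.

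- **The entry is cause-specific.** It begins "When diagnosing neurological deterioration due to index stroke, systemic reasons for deterioration" and excludes those reasons in order to isolate the infarct. Excluding haemorrhage serves the same purpose. This stands for deterioration that haemorrhage caused, but not for a bleed that is later or incidental.
- **The scan may mean the one taken at deterioration.** With an emergency CT required by 8.4, that is a natural reading. It is not what the sentence says, and a few words would settle it.
- **The patients are not lost.** A reader might infer that these events disappear from the trial. They do not. Early cases will mostly meet the IST-3 definition in 16.2.4, and all count as any intracranial haemorrhage. NIHSS change at 24 hours and day 7, death and the mRS carry no haemorrhage exclusion. Symptomatic haemorrhage alone does not recover every case: IST-3 stops at seven days, and SITS-MOST needs a type 2 parenchymal haematoma on the 22–36 hour scan plus a rise of at least 4 points, or haemorrhage leading to death. The progression count itself stays short.
- **The rates are assumed.** This stands. The increased risk in 3.1 is stated for rt-PA, and under independence the distortion is slight.

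A reader might also infer that the per-item threshold fills the outcome with false events, because a patient whose total NIHSS is falling can qualify. The documents do not support this. The wording shows a deliberate choice to count focal worsening, and no misclassification rate is given. False events common to both arms would pull a real benefit toward 1. With assumed true rates of 12% v 8%, adding 3–10% false events moves the OR from 0.64 to 0.70–0.79. That is opposite to the haemorrhage effect, so the net effect is undetermined.

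Nor should the rule be replaced by a rise in total NIHSS over the lowest earlier value. The recurrent-stroke entry (16.2.3) has no such reference. It appears only under SITS-MOST, "compared to baseline value or the lowest value between baseline and 24" hours, with a 4-point threshold. Section 9.1 schedules NIHSS only at baseline and at day 7 or discharge, and 10.2 adds 24 hours, so a lowest value would be poorly observed.

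**Conclusion.** The point holds as a weakness in one secondary outcome definition. As written, 16.2.6 conditions the progression count on a post-randomisation finding that thrombolysis is likely to make more frequent. The expected direction is toward tenecteplase.

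The direction rests on two premises: that the increase stated for rt-PA also applies to tenecteplase against no thrombolysis, and that some removed cases are infarct-driven. The size is not derivable from the documents. Under the assumed rates it runs from negligible (OR 0.95–0.98) to large (0.41–0.85). The large values are the full-overlap limit, not an expectation.

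A reader might go further and infer that the progression result will be biased by a known amount, or that the trial's main conclusion is at risk. Neither follows: the primary ordinal mRS analysis and N = 600 do not use this rule. The detailed Statistical Analysis Plan mentioned in Protocol 11.2 is not among the documents reviewed and may already settle the definition.

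**What to change.** In the Appendix and the Statistical Analysis Plan:

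1. State that 16.2.6 defines stroke progression.
2. Make the between-arm comparison on neurological deterioration of any neurological cause, infarct or haemorrhage, with systemic causes still excluded.
3. Have the blinded Event Adjudication Committee assign the cause (infarct, haemorrhage or both) as a second step, and report the split by arm descriptively.
4. Keep the index-stroke-only count as a supporting analysis. Exclude a case only when the haemorrhage is on a scan tied to the deterioration and is judged to explain it. Define significant.
5. Keep the per-item threshold, with a sensitivity analysis on total NIHSS if wanted.
6. Keep the 72-hour boundary with recurrent stroke from 16.2.3 and state it in 16.2.6, so that one event is not counted twice.

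The cost is wording and one adjudication field, with no added visit or scan. Sites must report every deterioration whatever the scan shows, so that the committee sees the cases the present rule would drop. The drawback is that some patients will appear under both progression and symptomatic haemorrhage; a table footnote should say so.

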### 16.2.7 Acute myocardial infarction

Either one of the following criteria satisfies the diagnosis of myocardial infarction:

1. Typical rise and gradual fall (troponin) or more rapid rise and fall (CK-MB) of biochemical markers of myocardial necrosis with at least one of the following:
  - a. ischaemic coronary symptoms;
  - b. development of pathologic Q waves on the ECG;
  - c. ECG changes indicative of ischemia (ST segment elevation or depression); or
  - d. coronary artery intervention (e. g. coronary angioplasty).
2. Autopsy pathologic findings of an acute myocardial infarction.

### 16.2.8 Major extracranial bleeding

Definition of major extracranial bleeding: Clinically overt bleeding associated with one or more of:

- Transfusion of  $>2$  red cell units of blood
- A decrease in haemoglobin of 20 g/l (=2 g/dl, = 1.24 mmol/l)
- Bleeding into retroperitoneum, intraocular space or major joint
- Bleeding leading to permanent treatment cessation

Otherwise, the bleeding will be characterized as minor.

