### **8.1 Open-label tenecteplase plus best standard care**

The total dose of tenecteplase is 0.25 mg per kg of body weight (maximum 25 mg). The dose shall be given as an intravenous bolus. Patients will be on bed rest in accordance with local routine following administration of tenecteplase.

After infusion, vital signs, neurological signs and blood pressure will be monitored every 15 minutes for two hours, then every 30 minutes for 6 hours, then 60 minutes until 24 hours from the start of treatment. Blood pressure should be maintained at or below 180/105 mmHg during the first 24 hours. Placement of intra-arterial catheters, indwelling bladder catheters, and nasogastric tubes shall be avoided for 24 hours if the patient can be safely managed without them. Venipunctures should be performed and monitored carefully.

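### The definition of major extracranial bleeding leaves out fatal bleeding, so a fatal bleed can be labelled minor, and its treatment-cessation criterion does not say which treatment is meant

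*Protocol*

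**What the plan says.** Section 10.2 of the Protocol lists "Major extra cranial bleeding" among the secondary clinical events and refers the reader to the Appendix for definitions. Section 16.2.8 then requires "Clinically overt bleeding associated with one or more of" four findings:

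1. transfusion of more than 2 "red cell units of blood";
2. a haemoglobin fall of 20 g/l;
3. "Bleeding into retroperitoneum, intraocular space or major joint";
4. "Bleeding leading to permanent treatment cessation".

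The section closes with a residual rule: "Otherwise, the bleeding will be characterized as minor".

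On treatment, section 8.1 states "The dose shall be given as an intravenous bolus". Section 8.2 gives the control arm no thrombolytic. Section 8.3 gives controls a loading dose of aspirin as soon as possible after randomisation. It withholds antiplatelet and anticoagulant drugs in tenecteplase patients until 24 hours have passed and the control CT is done, and then recommends the same daily aspirin dose in both arms.

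The 2018 version, in the combined protocol and SAP document, has neither this outcome nor this definition. Both are later additions and are current text.

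**The concern.** There are two separate weaknesses in one definition.

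First, death from the bleed is not a criterion, and the residual rule has no exception. The wording does not just leave a fatal bleed unaddressed; it assigns it to the minor class whenever the four criteria fail. In a trial of a thrombolytic against no thrombolytic, that understates the most serious extracranial events in the outcome meant to show them.

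Second, the cessation criterion would suit a drug given repeatedly. Here it has no stated object. Adjudicators must either ignore it or decide for themselves which treatment is meant, and the choice changes which bleeds count as major.

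**Working it through.** The question is one of wording, and the plan gives no figure to reproduce. The check applies the written rule to the possible cases and sets the relevant sections side by side.

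**Step 1: classify a fatal overt bleed.** Each of the four criteria is met or not met, giving 2 × 2 × 2 × 2 = 16 combinations. A bleed is major if at least one is met, so 15 combinations are major and 1 (none met) is minor. Whether the patient died does not enter the rule. The definition therefore permits a fatal bleed to be minor. The 1 in 16 counts logical cases; it is not a probability.

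**Step 2: see whether that case can arise.** A haemoglobin fall needs two values. Section 9.1 schedules blood tests on day 1 and on day 7 or discharge, and names haemoglobin only in the day 1 list. A patient who dies soon after the bleed starts may have no second value and no large transfusion, and the bleed may be at an unlisted site.

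**Step 3: apply each reading of the fourth criterion.**

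| Meaning of *treatment* | Can the criterion be met? | Fatal bleed that fails criteria 1 to 3 | Difference between arms from this criterion |
|---|---|---|---|
| Trial drug | No: a single bolus in one arm, nothing in the other | Minor | None |
| Background aspirin | Yes, if it is being taken and is stopped for good | Arguably major if on aspirin; minor if not | Possible in about the first 24 hours |

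On the first reading only three criteria operate: 2 × 2 × 2 = 8 combinations, of which 1 is still minor for a fatal bleed. Sections 8.1 and 8.3 mention an infusion in passing, but the administration specified is a bolus.

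On the second reading, only controls have protocol-directed aspirin to stop until the tenecteplase arm may begin. The control CT is set at 24 ± 6 hours after randomisation, that is 18 to 30 hours, so the gap is about one day. The trial is open-label, so the decision to stop is made by clinicians who know the allocation. Blinded adjudication under section 12.6 classifies the event afterwards but cannot undo that decision.

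**Step 4: compare with the rest of the Appendix.** In section 16.2.4 both definitions of symptomatic intracranial haemorrhage provide for death: the IST-3 definition counts death within seven days, with imaging evidence, and the SITS-MOST definition names haemorrhage that leads to death. Section 16.2.8 has no equivalent. Section 16.2.2 has seven cause-of-death categories and none is bleeding, so a fatal extracranial bleed would fall under another vascular or non-vascular cause, or unknown. It could then appear in no named outcome as a major or fatal bleed.

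**Step 5: check the units.** 20 g/l = 2 g/dl, and 20 / 1.24 = 16.1 g per mmol. The haemoglobin criterion shows no internal problem in its units.

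**The case against.** The gap is narrow. Many fatal bleeds would meet the transfusion or haemoglobin criterion. The haemoglobin criterion is not tied to scheduled samples, and section 8.4 asks investigators to carry out supplementary investigations of serious adverse events, so an unscheduled value will often exist. This stands, and it makes the misclassification uncommon. It does not remove it for a rapid death.

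The event is not lost. A fatal bleed is a serious adverse event under section 16.2.1, counts in all-cause death, and is within the six-monthly unblinded review under section 12.9. This also stands: only the label in one variable is at risk.

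The adjudication charter and the separate SAP mentioned in section 11.2 are not available here and may give further guidance. That is possible, but section 10.2 makes the Appendix the source of the definitions.

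Three stronger readings are tempting and should not be drawn:

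- A reader might infer that the definition both demotes fatal bleeds and promotes trivial ones. These effects rest largely on opposite meanings of *treatment*. If it means trial drug, the criterion adds no events in either arm. If it means aspirin, a fatal bleed in a patient taking aspirin could arguably count as major.
- A reader might infer a lasting imbalance between arms. The criterion requires permanent cessation, the stated aspirin rules differ only for about the first day, and follow-up is 3 months.
- A reader might attach a percentage. Assuming a rate of 0.5% to 2% in 300 patients gives 300 × 0.005 = 1.5 to 300 × 0.02 = 6 events, so one event is 1/300 = 0.33 percentage points, or 1/6 = 17% to 1/1.5 = 67% of the count. The rate is not in the documents, and the result is only the weight of any one event in a rare outcome. It does not show how often a fatal bleed would fail every criterion.

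**Conclusion.** The point holds in a limited form. As written, section 16.2.8 can class a rapidly fatal extracranial bleed as minor, and its cessation criterion is either empty or dependent on unblinded decisions, according to a meaning the Protocol does not give. It would be too strong to say that the criterion cannot be met at all: that is true only if *treatment* means the trial drug.

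The effect is confined to one secondary safety variable, and its size cannot be quantified from the documents. The mRS analysis and the sample size do not use this definition. The conclusion rests on the Appendix being the operative definition, as section 10.2 says, and on no further rule in a charter or SAP that could not be seen. It is still worth correcting, because the outcome concerns bleeding in a thrombolytic trial and the repair is small.

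**What to change.** In section 16.2.8, add fatal bleeding as a criterion for major extracranial bleeding. Then either delete the cessation criterion or define *treatment* so that the criterion applies equally in both arms. Deletion alone would not be enough: it would also remove the only route by which a fatal bleed that fails the other three criteria could count as major under the aspirin reading. The transfusion, haemoglobin and site criteria can stay as they are.

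Carry the same wording into the adjudication charter and the SAP, apply it to all events at blinded adjudication, and re-check any already adjudicated. The cost is a line or two in the Appendix and the charter, with no new data. Section 13.8 shows the adjudication committee as not yet appointed, so there may be few events, or none, to re-check.
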